**viii. Trial conduct and Data collection/management**

The coordinating centre for this trial will be Sunnybrook Health Sciences Centre where the study coordinator and central data clerk will be based. A physician lead will be available at SHSC to answer patients' questions about the study as well as acting as a resource for the site specific study coordinator regarding patient eligibility and education of required hospital staff. The master randomization list will be kept at SHSC.

Data will be collected on a customized case report form (CRF) that includes all relevant demographic and intra-operative data as well as each outcome sought. Patients will be provided with a home diary to complete that will capture all outcomes sought that are not obtained in hospital. CRFs and home diaries will be completely de-identified with only patient study number, age (in years), and gender as identifiers. Data from the CRFs will be entered into a database at each site on secure, password protected computers with hospital network backup. The master file linking identifying data (name, MRN, date of birth) and study number will be kept in a separate file on a secure, password protected computer with hospital network backup.

CRFs will be divided into 2 categories: "CRFs" and "Source-CRFs". "Source-CRFs" are the documents used by the RA or patient to directly capture study data. They include: the pain diary, side effect questionnaires and the sensory and motor block assessments. "CRFs" will be completed with data transcribed from a source document. They include: Preoperative details, intra-operative data collection and medication administered in the Post Anesthesia Care Unit (PACU) and Day Surgical Unit (DSU) all obtained from medical records.

### Data collection plan

Data will be collected according to the Source-CRFs/CRFs. All data collection will be conducted by a research staff member, either a research assistant or a co-investigator, who is blinded to the patient's treatment allocation.

1. Identifying information, exclusion criteria, surgical procedure description and anesthesia data will be collected preoperatively.
2. Procedure details, including: sedative used, procedure duration (end of injection), pain on injection and the presence of blood will be collected during the block procedure.
3. Pinprick sensation in the C4-T1 dermatomes at 10 and 20 minutes post block (to characterize presence/absence of block). Pain Sensation is characterized as a: (2) = sharp sensation, (1) = dull sensation only, or (0) = no sensation.
4. Motor function (elbow flexion for biceps) at 10 and 20 minutes post block. Power is graded using (2) = normal movement, (1) = reduced movement and (0) = no movement.
5. Intra-operative anesthesia data collection. Time of first Incision, administered anesthesia and time procedure ended.
6. Room air pulse oximetry 1 hour after admission to PACU/recovery room (to characterize respiratory function near discharge)
7. Blood Glucose level in PACU.
8. An account of analgesia administered in PACU.
9. Numerical rating scale (NRS) pain scores 1 hour after admission to PACU to PACU/recovery room
10. Information regarding post block complications (including pain and bruising around the block site) will be collected in a 1 week postoperative telephone call with the patient.
11. Time to first pain sensation in the shoulder, analgesic use and return of the affected hand to normal strength will be captured in the take home patient diary and reported at follow-up telephone calls.
12. NRS pain scores, analgesia consumption and side effects experienced will be captured at: 12hours/bed time, 24 hours and 7 days post-operatively in the patient's diary reported at follow-up telephone calls.

Upon achieving enrolment of the specified 180 patients and data is collected, the database will be verified, and analyzed by the biostatistician.

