**ii. Exclusion Criteria**

1. Lack of patient consent (including: inability to read or understand the ICF)
2. Allergy to dexamethasone or ropivacaine
3. BMI  $>$  35 kg/m^2

4. Contraindications to low dose dexamethasone including peptic ulcer disease, systemic infection, glaucoma, active varicella/herpetic infections, diabetes mellitus
5. Contraindications to ISB including severe Chronic Obstructive Pulmonary Disease (Forced expiratory volume < 40% predicted), coagulopathy, pre-existing neurologic deficit in ipsilateral upper extremity, localized infection
6. Pregnant or nursing females
7. Chronic opioid use defined as > 30mg oral morphine or equivalent per day
8. Unable to take acetaminophen or celecoxib

iii. **Protocol**

Patients scheduled for arthroscopic shoulder surgery will be approached for participation by research assistants in the pre-operative anesthetic clinic. Patients providing informed consent will be allocated 1:1 in blocks of 10 using a computer generated random number table (randomization will be stratified by site) and blinding of group allocation will be maintained with sequentially numbered, sealed, opaque envelopes.

**The following paragraph outlines standard of care practice (unless otherwise stated) for patients undergoing arthroscopic shoulder surgery at HoAC:**

On the day of surgery, patients will be pre-medicated with oral acetaminophen 1000mg, and oral celecoxib 400mg, unless otherwise stated by the attending physician. Once intravenous access is secure and standard monitors applied (electrocardiogram, non-invasive blood pressure cuff, continuous oxygen saturation), patients will receive sedation with intravenous midazolam (1-2mg). The lateral aspect of the neck including the supraclavicular fossa ipsilateral to the surgical site will be cleansed with standard isopropyl alcohol/chlorhexidine gluconate solution. The US-guided ISB will be performed under sterile conditions by a staff regional anesthesiologist, regional anesthesia fellow, or residents under supervision.

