**v. Secondary Outcomes**

- Time to first opioid consumption – from end of injection to time to first oral opioid consumption
- Duration of motor block - from end of injection to time of baseline preoperative biceps and hand strength
- Oxygen saturation on room air 1 hour after arrival to recovery room
- Opioid consumption on POD 1 at 12 hours/bed time if patient retires to bed before the 12hr time point), 24 hours and 7 days
- NRS for pain at 12hrs/Bed time (if patient retires to bed before the 12hr time point), 24hours, 7 days
- Blood glucose in recovery room
- Persistent paresthesia in the operative arm at 7 days
- Localized infection at block site at 7 days
- Postoperative nausea

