**vi. Sample size calculation**

Based on our clinical experience with low dose US-ISB (ropivacaine 0.5% 5ml) as well as previously published work, we expect mean sensory block duration of 12 hours with a standard deviation of 4 hours.

Based on the literature, we expect a mean prolongation of block time associated with perineural dexamethasone to be approximately 50% thereby increasing block duration to 18 hours. Defining an equivalency margin of 2 hours, we estimate that 87 patients per group (174 total) will be required to reliably test our hypothesis given  $\alpha=0.05$  and  $\beta=0.9$ . To account for incomplete data or loss to follow-up, the plan is to recruit 90 patients per group (180 total).

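### No pre-block pain score or numbness/tingling question is listed, so mild prior symptoms can dilute the day-7 paresthesia comparison and the NRS comparison loses some precision

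*Combined protocol and SAP*

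**What the plan says.** Section E.v lists among the secondary outcomes "Persistent paresthesia in the operative arm at 7 days" and "NRS for pain at 12hrs/Bed time (if patient retires to bed before the 12hr time point), 24hours, 7 days".

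The data collection plan in E.viii has one preoperative item, item 1: "Identifying information, exclusion criteria, surgical procedure description and anesthesia data will be collected preoperatively". The first sensory and motor checks (items 3 and 4) come 10 minutes after the block. The first NRS (item 9) comes 1 hour after arrival in recovery.

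Section E.ii, item 5, excludes patients with "pre-existing neurologic deficit in ipsilateral upper extremity". Because item 1 of the data collection plan includes the exclusion criteria, this is checked before the block. The criterion does not say whether numbness or tingling without other signs counts as a deficit.

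Section E.iii asks patients to record whether paresthesia, glossed as numbness or tingling, is present in the operative arm. The telephone calls also ask where it lies relative to the operative site. Neither asks whether the symptom is new. Section E.vii compares paresthesia by chi-square or Fisher's exact test and NRS by repeated measures ANOVA. It names no baseline covariate for either.

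**The concern.** The entry screen and the outcome use different terms. The screen asks about a neurologic deficit; the outcome records any numbness or tingling. A patient with occasional tingling can pass the first and be counted in the second, and no listed item would let the analyst separate that patient from one with a new symptom.

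This matters because perineural dexamethasone is off-label. Section C discusses neurotoxicity and persistent neuropathy, and day-7 paresthesia is the listed outcome closest to that question. Few events are likely, so one or two background cases per arm can change how the result reads. Section E.ix also asks for each adverse event to be coded for its association with the intervention, which is harder without knowing the arm's prior state.

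For pain, scores at 12 hours or bedtime, 24 hours and 7 days are compared with no preoperative score. Any between-patient variation that such a score would explain stays in the error term.

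**Working it through.** **1. The plan's own figure.** Section E.vi states: "we expect mean sensory block duration of 12 hours with a standard deviation of 4 hours", and "Defining an equivalency margin of 2 hours, we estimate that 87 patients per group (174 total) will be required". Two one-sided tests, 0.05 each, power 0.90 (the plan writes this as β = 0.9), true difference 0:

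n = 2 × [SD × (z₀.₉₅ + z₀.₉₅) / margin]² = 2 × [4 × (1.645 + 1.645) / 2]² = 86.6, so 87 per group.

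This matches. Power is 90.2% at 87 and 91.3% at the planned 90 per group. No input depends on a pre-block NRS or paresthesia item, so this point does not affect the primary analysis.

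**2. Paresthesia: small counts.** Input: 90 per arm (E.vi). Assumptions: the number of enrolled patients with prior symptoms, and that every such symptom persists and is reported at day 7. The documents give no figure for either. Two-sided Fisher's exact test:

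| Prior cases per arm | Counted events | p |
|---|---|---|
| 0 | 0 v 6 | 0.029 |
| 1 | 1 v 7 | 0.064 |
| 3 | 3 v 9 | 0.13 |

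The excess is six patients in every row; only the background changes. Not every split crosses 0.05. A true 0 v 5 gives p = 0.059 and, with three prior cases per arm, 3 v 8 gives p = 0.21; neither is below 0.05.

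**3. Paresthesia: power over a range.** With prior prevalence b, the observed rate is q = b + (1 − b) × p, where p is the new-event rate. Assumed p is 5% v 15%, with 90 per arm and a two-sided 0.05 test of proportions. The last column sets the prior cases aside, leaving 90 × (1 − b) per arm.

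| b | Observed rates | Risk ratio | Power, all counted | Power, prior cases set aside |
|---|---|---|---|---|
| 0 | 5.0% v 15.0% | 3.0 | 61% | 61% |
| 2% | 6.9% v 16.7% | 2.4 | 53% | 60% |
| 5% | 9.8% v 19.3% | 2.0 | 44% | 59% |
| 10% | 14.5% v 23.5% | 1.6 | 34% | 57% |

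The risk difference barely moves (10.0 points at b = 0, 9.0 at b = 10%). The loss comes mainly from the higher background rate. The exclusion criterion should keep b towards the top of this table, but the documents do not say how low.

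**4. NRS: precision.** With a baseline covariate correlated r with the follow-up score, residual variance is multiplied by 1 − r² and the standard error by √(1 − r²). The value of r is assumed.

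| r | 1 − r² | Cut in standard error | 90 per arm worth, 90 / (1 − r²) |
|---|---|---|---|
| 0.1 | 0.99 | 0.5% | 91 |
| 0.2 | 0.96 | 2.0% | 94 |
| 0.3 | 0.91 | 4.6% | 99 |
| 0.4 | 0.84 | 8.3% | 107 |
| 0.5 | 0.75 | 13.4% | 120 |

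One r need not hold at every time point. Section E.vi expects blocks of 12 to 18 hours, so the 12-hour score may be taken while the block still works. The gain is probably smallest there.

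**The case against.** The best defence is that prior arm symptoms are already handled. The deficit exclusion applies to the operative arm and is recorded preoperatively under the same item that lacks the symptom question. A reader might infer that every symptom present before surgery is counted as a post-block event. The documents do not support that: only symptoms short of an excluded deficit can get through.

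A reader might also infer that these symptoms are never recorded before the block. That goes too far. Section E.viii mentions a form for preoperative details whose contents are not itemised, and says the case report form covers each outcome sought. What can be said is that the data collection plan lists neither item. The form is transcribed from medical records, so nothing in the plan makes a standard NRS or tingling question part of it.

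The outcome is called persistent, and the calls collect it among side effects and complications, which suggests symptoms that follow the block. But no text requires the symptom to be new.

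A third tempting reading is bias between arms. Allocation is randomised 1:1, so baseline pain and tingling are expected to balance and the unadjusted NRS comparison is valid. Nor do the documents say that these patients have a painful shoulder; the criterion is arthroscopic shoulder surgery. The NRS gain could therefore lie at the low end of the range.

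Finally, the trial is sized on block duration, not on paresthesia or NRS. That stands, and it limits the priority of the point.

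**Conclusion.** The point holds in a limited form. The entry screen is narrower than the day-7 outcome, so mild or intermittent prior symptoms can be counted as events. The expected effect is dilution in both arms, which would tend to hide an excess from the perineural route. In the worked example one prior case per arm moves p from 0.029 to 0.064. At assumed new-event rates of 5% v 15%, a 2% to 5% prior prevalence lowers power from 61% to between 53% and 44%. The NRS comparison is unbiased but gives up 0.5% to 13% of its standard error for r between 0.1 and 0.5.

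Prevalence, persistence of prior symptoms, event rates and correlation are all assumptions. Only secondary outcomes are touched, so the priority is low to moderate.

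**What to change.** 1. Add two questions to item 1 of the data collection plan, asked before sedation and before the block: current NRS pain in the operative shoulder; and any numbness or tingling in the operative arm (yes/no and location).
2. In E.v, define the day-7 outcome as paresthesia that is new or worsened since that assessment.
3. In E.vii, include preoperative NRS as a covariate in the repeated-measures model for NRS.

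The cost is about a minute per patient on an existing form and one extra model term. There is no extra visit and no change to sample size or treatment. Patients already enrolled would lack the values; the plan should say how they are handled, since a pre-block state cannot be recovered reliably afterwards.

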#### **ix. Data safety monitoring plan**

This study involves the off-label use of dexamethasone. Consequently, an application to Health Canada will be made to obtain regulatory approval for the use of perineural dexamethasone. All adverse events will be documented (serious or not, related or not, expected or not) and reported following the Site

Guidance on Safety Reporting document. Serious adverse events are not expected. The severity of the adverse event will be coded as mild, moderate, or severe. The association with the intervention will be coded as unrelated, unlikely related, possibly related, probably related, or definitely related. The principal investigator will review all adverse events and act as safety monitor. These will be communicated to Health Canada and the Research Ethics Board of each respective institution. The independent reviewers will determine if the off-label use of dexamethasone contributed in any way to the adverse event and will make recommendations to either terminate, or modify study protocols.

The following are potential side effects often associated with surgical procedures that are not considered adverse events related to this study (obtained confirmation from five other physicians who declare no conflict of interest) and will therefore not need to be assessed and recorded by the QI in cases where these side effects are reported by study patients while they are in hospital and at home during post-operative follow-up telephone interviews:

- Headache/dizziness/nausea/vomiting/wheezing
- Bruising in the arm
- Gritty feeling in the eye/blurred vision/mild visual disturbance
- Bradycardia/tachycardia
- Complications associated with general anesthesia such as major cardiac events
- Local anesthetic toxicity
- Hemidiaphragmatic paresis (temporary)
- Hoarse voice (temporary)
- Horner's syndrome (temporary)
- Pruritus
- Changes in blood pressure
- Oxygen saturation below 90%
- Pain, cellulitis, or muscle spasm in areas other than the nerve block injection

A single interim analysis will be performed at 50% enrolment. If the data analysis indicates equipoise no longer exists, the study will be stopped early. The Haybittle-Peto threshold will be utilized (p=0.001).

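### The safety plan documents every adverse event, yet exempts 13 patient-reported list entries from QI assessment and recording, with no exception for serious cases and no stated order of precedence

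*Combined protocol and SAP*

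**What the plan says.** Section E.ix opens with a general rule: "All adverse events will be documented (serious or not, related or not, expected or not". The same sentence sends those events for reporting under the Site Guidance on Safety Reporting document. Each event is coded for severity and, on a five-level scale, for association with the intervention. "The principal investigator will review all adverse events and act as safety monitor". Further on, "The independent reviewers will determine if the off-label use of dexamethasone contributed in any way to the adverse event". The section also states that serious adverse events are not expected.

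Section E.iii (Protocol) covers the telephone follow-up on days 1 and 7. An adverse event mentioned in a call goes into the adverse event log and is assessed by the QI. Serious adverse events and adverse reactions may prompt further calls and are reported under the Site Guidance document.

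Section E.ix then gives a list of side effects often seen with surgery "that are not considered adverse events related to this study". The protocol says that five other physicians without a conflict of interest confirmed this. The listed items "will therefore not need to be assessed and recorded by the QI in cases where these side effects are reported by study patients", either in hospital or in the follow-up calls. Among the 13 bullets are "Complications associated with general anesthesia such as major cardiac events", "Local anesthetic toxicity" and "Oxygen saturation below 90" per cent.

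**The concern.** The general rule, the telephone rule and the exemption give different instructions for the same event. If a patient reports a listed event in a follow-up call, section E.iii has the QI assess it and section E.ix says the QI need not. The reason given for the exemption is that the events are unrelated, but the opening rule of the same section applies to events whether related or not.

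Staff who follow the list as written could leave a serious patient-reported event without QI assessment and without an association code. The perineural route is off-label and needs a Health Canada application, and independent reviewers are meant to judge whether dexamethasone contributed to an event. An event that is ruled unrelated in advance, and never assessed, may not reach that judgement.

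**Working it through.** The plan states no figure on this point, so the check compares the texts and counts the list.

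**1. The rules side by side**

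| Rule | Place | Applies to | Instruction |
|---|---|---|---|
| General | E.ix, opening | All adverse events, whatever their seriousness, relatedness or expectedness | Document, report under the Site Guidance document, code severity and association |
| Telephone | E.iii, follow-up | Any adverse event mentioned in a call | Log, and have the QI assess |
| Exemption | E.ix, list | 13 bullets, when reported by patients in hospital or by telephone | No QI assessment or recording needed |

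The exemption overlaps the general rule in both settings and the telephone rule in the calls.

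**2. Does the stated reason support the exemption?** The reason is unrelatedness. The general rule includes unrelated events, so unrelatedness does not remove an event from it. Expectedness does not either, because the general rule includes expected events. The list also settles association in advance for whole classes of event, whereas the general rule codes it event by event.

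**3. Are serious cases kept out of the list?** Of the 13 bullets, three are limited to temporary events (hemidiaphragmatic paresis, hoarse voice, Horner's syndrome) and one contains the word mild (visual disturbance): 3 + 1 = 4 with some limit, and 13 − 4 = 9 with no limit of duration or severity. The general-anesthesia, local anesthetic toxicity and oxygen saturation entries are among the 9. Bullets with an exception for serious cases: 0 of 13.

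**4. Does any text rank the rules?** Two places bear on it: the Site Guidance clause in the opening rule of E.ix, and the sentence on serious events and adverse reactions in E.iii. Neither mentions the list, and the list mentions neither. The documents also do not say whether the QI and the principal investigator are the same person, or whether an exempt event still reaches the principal investigator's review.

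**5. What is captured in other ways?**
- Events observed by staff fall outside the exemption, which is confined to patient reports.
- Nausea and room-air oxygen saturation one hour after arrival in recovery are secondary outcomes (E.v).
- The telephone calls ask about side effects or complications (E.iii). The examples given concern the operative arm and the block site, and the protocol adds that nothing further will be asked.
- Side effect questionnaires are source documents (E.viii).
- The data collection plan in E.viii collects post-block complications at one week (item 10) and side effects at 12 hours or bedtime, 24 hours and 7 days (item 12).

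A listed event may therefore be noted somewhere. None of these routes names major cardiac events or local anesthetic toxicity, and none is said to supply QI assessment or association coding.

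**The case against.** The strongest reply is that the list is a specific exception to a general rule, and that the safety plan names a controlling document. The opening rule of E.ix sends all adverse events to the Site Guidance document, which may define seriousness and override the list. On that view only a cross-reference is missing. The list was also confirmed by five physicians, and much of what it covers would be seen first by staff, since patients are monitored at the block and anesthetized under attending care.

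Much of this stands. The Site Guidance document may well settle precedence, and its absence here is no fault of the plan. Staff observation narrows the exposure for oxygen saturation, and for cardiac or toxic events around the block and surgery. What remains is a serious event that the patient reports, chiefly after discharge. The exception reading also leaves the words on related and unrelated events in place and does not say what happens to a serious listed event. The physicians are said to have confirmed that the items are not study-related; that does not say which rule prevails.

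A reader might infer that serious events on the list will go unrecorded altogether. The documents do not support that. The exemption concerns the QI and patient reports only, and other routes of capture exist. A reader might also infer that the cardiac and local anesthetic toxicity entries must come off the list. The contradiction does not require it once seriousness overrides the list.

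**Conclusion.** The concern holds as an internal inconsistency that should be fixed. The general and telephone rules conflict with the exemption, the reason given for the exemption is one that the general rule does not accept, and no supplied text says which prevails. The consequence is confined to missing QI assessment and association coding for a serious patient-reported event on the list.

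The wording conflict is certain from the text. The loss of a serious event from assessment is only possible, and rests on two assumptions: that the Site Guidance document contains no override, and that staff apply the list as written. The documents give no event rates, so the number of events affected cannot be calculated. The primary analysis of block duration is unaffected.

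**What to change.** Reconcile sections E.iii and E.ix on recording and assessment:

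1. State in E.ix that any event meeting seriousness criteria, listed or not and however reported, is recorded, assessed for relatedness and reported under the Site Guidance document.
2. Limit the exemption to non-serious expected events.
3. Refer to that exemption in the opening rule of E.ix and in the telephone rule of E.iii, so that all three statements agree.

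If the Site Guidance document already contains such an override, citing it beside the list would serve for item 1.

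The cost is a few sentences and some additional adverse event log entries, whose number cannot be derived from the documents. No visits, procedures or patients are added, and the primary analysis does not change.

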**vii. Statistical analysis**

Demographic data will be summarized and expressed using appropriate measures of central tendency and dispersion for continuous data, means and standard deviations will be provided (medians and interquartile ranges for non-normally distributed data) and for categorical data counts and percentages will be displayed. The primary outcome, time to first sensation of pain at the surgical site, will be compared between the two groups using a two sample equivalence test of means. Secondary outcomes that are time based will also be assessed in the above manner (time to first analgesic request, duration of motor block). Continuous secondary outcomes (opioid consumption, NRS) will be assessed with repeated measures ANOVA while blood glucose will be assessed with the t-test. Categorical outcomes (paresthesia,

infection, nausea) will be compared with the Chi square or Fisher's exact test for the case of low expected cell counts.

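### Does the interim p=0.001 rule need rewriting because it names no outcome, null hypothesis or sidedness?

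*Combined protocol and SAP*

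**What the plan says.** The interim look takes up three sentences at the end of E.ix, Data safety monitoring plan. They give the timing ("A single interim analysis will be performed at 50% enrolment"), the criterion ("If the data analysis indicates equipoise no longer exists, the study will be stopped early") and the boundary ("The Haybittle-Peto threshold will be utilized (p=0.001"). The same section says "Serious adverse events are not expected".

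The other statistical sections do not refer to the look. E.vi gives the design figures: "Defining an equivalency margin of 2 hours, we estimate that 87 patients per group (174 total) will be required", with SD 4 h and α 0.05. E.vii says that the primary outcome "will be compared between the two groups using a two sample equivalence test of means" and that categorical outcomes "will be compared with the Chi square or Fisher's exact test for the case of low expected cell counts". The Data collection plan in E.viii describes the final analysis: "Upon achieving enrolment of the specified 180 patients and data is collected, the database will be verified, and analyzed by the biostatistician".

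**The concern.** A stopping rule should give one answer for one data set, and that answer should be fixed before anyone looks. Here the wording fits several tests: no difference in block duration (one- or two-sided), equivalence, a difference larger than the margin, or a safety outcome, since the rule sits in the safety section. An observed 3.0 h difference at the look gives p = 0.0006 against no difference (stop) but p = 0.12 against the 2 h margin (continue).

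If the test were chosen after the interim results were known, the decision could follow the data. What the trial could then say about non-equivalence would also vary. A stop exactly at 2.87 h leaves a 90% interval of about 1.5 to 4.3 h, which includes values inside the margin. Section C promises that a finding of non-equivalence will inform practice, so this is a fair question to ask.

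**Working it through.** **Inputs.** Margin 2 h, SD 4 h, α 0.05 and 90 per group recruited (E.vi); one look at half enrolment (E.ix), so 90/2 = 45 per group. Assumed: complete data at the look, normal outcomes, equal SDs and a symmetric margin of ±2 h. SDs of 3 h and 5 h are assumed for sensitivity.

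**The plan's own figure.** For two one-sided 0.05 tests, 90% power and a true difference of 0, n = 2 × [4 × (1.645 + 1.645)/2]² = 86.58, so 87 per group. This matches E.vi exactly and shows that the trial is planned around no true difference between routes.

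**Boundaries at the look.** SE = 4 × √(2/45) = 0.843 h, with 88 degrees of freedom.

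- No difference, two-sided: 3.405 × 0.843 = 2.87 h.
- No difference, one-sided: 3.185 × 0.843 = 2.69 h.
- Beyond the margin, one-sided: 2 + 2.69 = 4.69 h.
- Equivalence: the observed difference would have to be below 2 − 2.69 = −0.69 h in absolute value, which is impossible at an observed SD of 4 h. The smallest p, at an observed 0 h, is P(t > 2/0.843 = 2.37) = 0.0099.
- Binary safety outcome, Fisher's exact test: 0 vs 10 of 45 gives p = 0.0011 and 0 vs 11 gives p = 0.0005, so at least 11 vs 0 is needed.

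**How often the difference and margin readings conflict.** Simulation of 1,000,000 two-stage trials per row (45 + 45 per group, pooled-variance t-tests), SD 4 h:

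| True difference | Two-sided difference test stops | Margin test stops | Opposite decisions |
|---|---|---|---|
| 0 h | 0.1% | under 0.01% | 0.1% |
| 1 h | 1.6% | under 0.01% | 1.6% |
| 2 h | 16% | 0.1% | 16% |
| 3 h | 56% | 2.6% | 54% |
| 4 h | 90% | 22% | 69% |
| 6 h | 100% | 94% | 6% |

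One- and two-sided difference tests disagree in at most about 8% of trials (at 3 h).

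**Effect on the equivalence conclusion.** A difference stop cannot produce a false equivalence claim; it can only remove a true one. At SD 4 h the trials that stop and would otherwise have shown equivalence are about 0.03% or fewer at any true difference from 0 to 1.5 h. At SD 3 h the largest loss is about 0.5%, at 1 h.

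**Effect on statements about non-equivalence.** Chance that the final 90% interval lies wholly beyond 2 h when the true difference is 3 h:

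| SD | Difference test at the look | Margin test at the look |
|---|---|---|
| 3 h | 49% | 72% |
| 4 h | 42% | 51% |
| 5 h | 40% | 38% |

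**The equivalence reading at a smaller SD.** At SD 3 h and a true 0 h, about 7% of trials would reach an equivalence p of 0.001, because the observed SD varies from trial to trial. The reading is therefore inert at SD 4 h but not at every SD.

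**The case for a change.** The strongest case for a change is that each obvious way of filling the gap has a weakness. Carrying over the equivalence test from E.vii makes the rule almost inert at the planned SD. A plain difference test is not stated, and section C criticises an earlier trial for drawing an equivalence conclusion without margins. A safety reading names no outcome. Any observed difference between about 2.9 and 4.7 h stops or continues depending on the choice, and one or two sentences would settle it.

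Part of this stands. The text does not fix the test, and the choice could in principle be made with interim results in hand; E.iii keeps the statisticians blinded, which limits that risk without removing it. But the 2.9 to 4.7 h conflict needs a test against the margin at the look, which no section mentions. Without that reading, the remaining live choice at SD 4 h is sidedness, 2.69 against 2.87 h. The 12 h and 18 h in E.vi compare block alone with added perineural dexamethasone, so they do not predict a 3 to 4 h gap between routes. The loss of information under a difference test is real at SD 3 h and 4 h, but at SD 5 h and a true 3 h it slightly reverses.

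**Conclusion.** The omission is real, but no change to the plan follows. A Haybittle-Peto boundary tied to lost equipoise is most naturally applied as a test of difference on the primary outcome. An analyst who does so two-sided at 0.001 gets a workable rule that stops 0.1% of trials when the routes do not differ and leaves the equivalence conclusion almost untouched (about 0.03% of trials or fewer at SD 4 h, at most about 0.5% at SD 3 h). Preferring the margin test would be a trade-off rather than a correction. At a true 4 h and SD 4 h it raises the chance of an interval wholly beyond 2 h from 83% to 95.5%, but stops only 22% of trials at the look instead of 90%.

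These figures assume 45 evaluable patients per group and normal outcomes. With 43 per group the boundaries move only to 2.94, 2.75 and 4.75 h. If the true difference were 3 to 4 h, the choice of test would matter more, chiefly for how firmly non-equivalence could be stated. Recording the test before the look is ordinary good practice and needs no redesign.
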